**Table 7: Collapsed Comparisons of the Proportion of Participants Experiencing Adverse Events by Event Type**

Event Type	200 µg ALFQ (N=X)	100 µg ALFQ (N=X)	50 µg ALFQ (N=X)	p-value
	n (%)	n (%)	n (%)	
Solicited Adverse Events				
Any Solicited Symptom	x (x.x)	x (x.x)	0.xx	0.xx
Mild (grade 1) b	x (x.x)	x (x.x)	0.xx	0.xx
Moderate (Grade 2) b	x (x.x)	x (x.x)	0.xx	0.xx
Severe (Grade 3) b	x (x.x)	x (x.x)	0.xx	0.xx
Potentially Life Threatening (Grade 4) b	x (x.x)	x (x.x)	0.xx	0.xx
Any Systemic Symptom	x (x.x)	x (x.x)	0.xx	0.xx
Mild (grade 1) b	x (x.x)	x (x.x)	0.xx	0.xx
Moderate (Grade 2) b	x (x.x)	x (x.x)	0.xx	0.xx
Severe (Grade 3) b	x (x.x)	x (x.x)	0.xx	0.xx
Potentially Life Threatening (Grade 4) b	x (x.x)	x (x.x)	0.xx	0.xx
Any Local Symptom	x (x.x)	x (x.x)	0.xx	0.xx
Mild (grade 1) b	x (x.x)	x (x.x)	0.xx	0.xx
Moderate (Grade 2) b	x (x.x)	x (x.x)	0.xx	0.xx
Severe (Grade 3) b	x (x.x)	x (x.x)	0.xx	0.xx
Potentially Life Threatening (Grade 4) b	x (x.x)	x (x.x)	0.xx	0.xx
Unsolicited Adverse Events				
Any Serious Adverse Event	x (x.x)	x (x.x)	0.xx	0.xx
Any Adverse Event of Special Interest	x (x.x)	x (x.x)	0.xx	0.xx
Any Related, Unexpected Adverse Event	x (x.x)	x (x.x)	0.xx	0.xx
Any Unexpected Adverse Event Within 28 Days of Study Vaccination	x (x.x)	x (x.x)	0.xx	0.xx
Note: N = Number of participants in the Safety Population; n = Number of participants reporting each symptom a Exact binomial tests used				
b Maximum severity reported				

**SOLICITED ADVERSE EVENTS****Table 8: Number and Percentage of Participants Experiencing Solicited Reactogenicity Events with 95% Confidence Intervals, by Event and Vaccination Group**

Event	200 µg ALFQ (N=X)			100 µg ALFQ (N=X)			50 µg ALFQ (N=X)			All Participants (N = X)		
	n	%	95% CI	n	%	95% CI	n	%	95% CI	n	%	95% CI
Any Reactogenicity	X	X.X	X.X, X.X	X	X.X	X.X, X.X	X	X.X	X.X, X.X	X	X.X	X.X, X.X
Any Systemic Reactogenicity	X	X.X	X.X, X.X	X	X.X	X.X, X.X	X	X.X	X.X, X.X	X	X.X	X.X, X.X
[Systemic Event 1]	X	X.X	X.X, X.X	X	X.X	X.X, X.X	X	X.X	X.X, X.X	X	X.X	X.X, X.X
[Systemic Event 2]	X	X.X	X.X, X.X	X	X.X	X.X, X.X	X	X.X	X.X, X.X	X	X.X	X.X, X.X
Any Local Reactogenicity	X	X.X	X.X, X.X	X	X.X	X.X, X.X	X	X.X	X.X, X.X	X	X.X	X.X, X.X
[Local Event 1]	X	X.X	X.X, X.X	X	X.X	X.X, X.X	X	X.X	X.X, X.X	X	X.X	X.X, X.X
[Local Event 2]	X	X.X	X.X, X.X	X	X.X	X.X, X.X	X	X.X	X.X, X.X	X	X.X	X.X, X.X
Note: N = Number of participants in the Safety Population												

**Table 9: Number and Percentage of Participants Experiencing Solicited Reactogenicity Events by Event, Maximum Severity, and Vaccination Group**

Event	Severity	200 µg ALFQ (N=X)		100 µg ALFQ (N=X)		50 µg ALFQ (N=X)	
		n	%	n	%	n	%
							X.X

Any Reactogenicity	None	X	X.X	X	X.X	X	X.X
	Mild	X	X.X	X	X.X	X	X.X
	Moderate	X	X.X	X	X.X	X	X.X
	Severe	X	X.X	X	X.X	X	X.X
	Potentially Life Threatening						
Systemic Reactogenicity							
Any Systemic Reactogenicity	None	X	X.X	X	X.X	X	X.X
	Mild	X	X.X	X	X.X	X	X.X
	Moderate	X	X.X	X	X.X	X	X.X
	Severe	X	X.X	X	X.X	X	X.X
	Potentially Life Threatening						
[Systemic Event 1]	None	X	X.X	X	X.X	X	X.X
	Mild	X	X.X	X	X.X	X	X.X
	Moderate	X	X.X	X	X.X	X	X.X
	Severe	X	X.X	X	X.X	X	X.X
	Potentially Life Threatening						
[Systemic Event 2]	None	X	X.X	X	X.X	X	X.X
	Mild	X	X.X	X	X.X	X	X.X
	Moderate	X	X.X	X	X.X	X	X.X
	Severe	X	X.X	X	X.X	X	X.X
	Potentially Life Threatening						
Local Reactogenicity							
Any Local Reactogenicity	None	X	X.X	X	X.X	X	X.X
	Mild	X	X.X	X	X.X	X	X.X
	Moderate	X	X.X	X	X.X	X	X.X
	Severe	X	X.X	X	X.X	X	X.X
	Potentially Life Threatening						
[Local Event 1]	None	X	X.X	X	X.X	X	

Event	Severity	200 µg ALFQ (N=X)		100 µg ALFQ (N=X)		50 µg ALFQ (N=X)	
		n	%	n	%	n	%
	Mild	X	X.X	X	X.X	X	X.X
	Moderate	X	X.X	X	X.X	X	X.X
	Severe	X	X.X	X	X.X	X	X.X
	Potentially Life Threatening						
[Local Event 2]	None	X	X.X	X	X.X	X	X.X
	Mild	X	X.X	X	X.X	X	X.X
	Moderate	X	X.X	X	X.X	X	X.X
	Severe	X	X.X	X	X.X	X	X.X
	Potentially Life Threatening						

Note: N = Number of participants in the Safety Population who received the specified dose; n = Number of participants reporting each event; severity is the maximum severity reported post dosing for each participant for each day.

**UNSOLICITED ADVERSE EVENTS****Table 10: Summary of Unsolicited Adverse Events by System Organ Class and Preferred Term, and Vaccination Group**

System Organ Class	Preferred Term	200 µg ALFQ (N=X)				100 µg ALFQ (N=X)				50 µg ALFQ (N=X)			
		n	%	95% CI	Events	n	%	95% CI	Events	n	%	95% CI	Events
Serious Adverse Events													
Any	Any	X	X.X	X.X, X.X	X	X	X.X	X.X, X.X	X	X	X.X	XX, XX	X
[SOC 1]	Any	X	X.X	X.X, X.X	X	X	X.X	X.X, X.X	X	X	X.X	XX, XX	X
	[PT 1]	X	X.X	X.X, X.X	X	X	X.X	X.X, X.X	X	X	X.X	XX, XX	X
	[PT 2]	X	X.X	X.X, X.X	X	X	X.X	X.X, X.X	X	X	X.X	XX, XX	X
[SOC 2]	Any	X	X.X	X.X, X.X	X	X	X.X	X.X, X.X	X	X	X.X	XX, XX	X
	[PT 1]	X	X.X	X.X, X.X	X	X	X.X	X.X, X.X	X	X	X.X	XX, XX	X
	[PT 2]	X	X.X	X.X, X.X	X	X	X.X	X.X, X.X	X	X	X.X	XX, XX	X
Adverse Events of Special Interest													
Any	Any	X	X.X	X.X, X.X	X	X	X.X	X.X, X.X	X	X	X.X	XX, XX	X
[SOC 1]	Any	X	X.X	X.X, X.X	X	X	X.X	X.X, X.X	X	X	X.X	XX, XX	X
	[PT 1]	X	X.X	X.X, X.X	X	X	X.X	X.X, X.X	X	X	X.X	XX, XX	X
	[PT 2]	X	X.X	X.X, X.X	X	X	X.X	X.X, X.X	X	X	X.X	XX, XX	X
[SOC 2]	Any	X	X.X	X.X, X.X	X	X	X.X	X.X, X.X	X	X	X.X	XX, XX	X
	[PT 1]	X	X.X	X.X, X.X	X	X	X.X	X.X, X.X	X	X	X.X	XX, XX	X
	[PT 2]	X	X.X	X.X, X.X	X	X	X.X	X.X, X.X	X	X	X.X	XX, XX	X
Other Non-Serious Unsolicited Adverse Events													
Any	Any	X	X.X	X.X, X.X	X	X	X.X	X.X, X.X	X	X	X.X	XX, XX	X
[SOC 1]	Any	X	X.X	X.X, X.X	X	X	X.X	X.X, X.X	X	X	X.X	XX, XX	X
	[PT 1]	X	X.X	X.X, X.X	X	X	X.X	X.X, X.X	X	X	X.X	XX, XX	X

System Organ Class	Preferred Term	200 µg ALFQ (N=X)				100 µg ALFQ (N=X)				50 µg ALFQ (N=X)			
		n	%	95% CI	Events	n	%	95% CI	Events	n	%	95% CI	Events
	[PT 2]	X	X.X	X.X, X.X	X	X	X.X	X.X, X.X	X	X	X.X	XX, XX	X
[SOC 2]	Any PT	X	X.X	X.X, X.X	X	X	X.X	X.X, X.X	X	X	X.X	XX, XX	X
	[PT 1]	X	X.X	X.X, X.X	X	X	X.X	X.X, X.X	X	X	X.X	XX, XX	X
	[PT 2]	X	X.X	X.X, X.X	X	X	X.X	X.X, X.X	X	X	X.X	XX, XX	X

**Note:** N = Number of participants in the Safety Population; n = Number of participants reporting each SOC/PT. A participant is only counted once per PT.

**Table 11: Number and Percentage of Participants Experiencing Unsolicited Adverse Events by System Organ Class and Preferred Term, Maximum Severity, Relationship, and Vaccination Group**

System Organ Class	Preferred Term	Any Incidence		Severity 			Potentially Life Threatening		Not Related		Relationship to Treatment 		
				Mild	Moderate	Severe							
		n	%	n	%	n	%	n	%	n	%	n	%
200 µg ALFQ (N=X)													
Any	Any PT	x	XX	x	XX	x	XX	x	XX	x	XX	x	XX
[SOC 1]	Any PT												
	[PT 1]												
	[PT 2]												
[SOC 2]	Any PT												
	[PT 1]												
	[PT 2]												
100 µg ALFQ (N=X)													
Any	Any PT	x	XX	x	XX	x	XX	x	XX	x	XX	x	XX
[SOC 1]	Any PT												
	[PT 1]												
	[PT 2]												
[SOC 2]	Any PT												
	[PT 1]												
	[PT 2]												
50 µg ALFQ (N=X)													
Any	Any PT	x	XX	x	XX	x	XX	x	XX	x	XX	x	XX
[SOC 1]	Any PT												
	[PT 1]												
	[PT 2]												
[SOC 2]	Any PT												
	[PT 1]												
	[PT 2]												
	Note: N = Number of participants in the Safety Population.  For severity, a participant is counted once per preferred term and is summarized according to the highest reported severity.  For relationship, a participant is only counted once per preferred term and is summarized according to the closest reported relationship.												

**Table 12: Summary of Clinical Laboratory Results by Parameter, Maximum Severity, Visit, and Vaccination Group – [Parameter]**

Visit	Vaccination Group	N	None		Mild / Grade 1		Moderate/ Grade 2		Severe/ Grade 3		Potentially Life Threatening/ Grade 4		Missing	
			n	%	n	%	n	%	n	%	n	%	n	%
Baseline (Day 0)	200 µg ALFQ	x	x	x.x	x	x.x	x	x.x	x	x.x	x	x.x	x	x.x
	100 µg ALFQ	x	x	x.x	x	x.x	x	x.x	x	x.x	x	x.x	x	x.x
	50 µg ALFQ	x	x	x.x	x	x.x	x	x.x	x	x.x	x	x.x	x	x.x
[Additional visits]	200 µg ALFQ	x	x	x.x	x	x.x	x	x.x	x	x.x	x	x.x	x	x.x
	100 µg ALFQ	x	x	x.x	x	x.x	x	x.x	x	x.x	x	x.x	x	x.x
	50 µg ALFQ	x	x	x.x	x	x.x	x	x.x	x	x.x	x	x.x	x	x.x
Max Severity Post Baseline	200 µg ALFQ	x	x	x.x	x	x.x	x	x.x	x	x.x	x	x.x	x	x.x
	100 µg ALFQ	x	x	x.x	x	x.x	x	x.x	x	x.x	x	x.x	x	x.x
	50 µg ALFQ	x	x	x.x	x	x.x	x	x.x	x	x.x	x	x.x	x	x.x
Note: The “Max Post Baseline” rows indicate the maximum severity experienced by each participant at any time point post baseline, including unscheduled assessments. N = Number of participants in the Safety Population with available samples; n = Number of participants reporting each severity														

**Table 13: Clinical Laboratory Summary Statistics by Visit and Vaccination Group  
– [Parameter]**

Time Point	Vaccination Group	N	Mean	Standard Deviation	Median	Min, Max
Baseline (Day 0)	200 µg ALFQ	x	xx.x	xx.x	xx.x	xx.x, xx.x
	100 µg ALFQ	x	xx.x	xx.x	xx.x	xx.x, xx.x
	50 µg ALFQ	x	xx.x	xx.x	xx.x	xx.x, xx.x
[Additional visits]	200 µg ALFQ	x	xx.x	xx.x	xx.x	xx.x, xx.x
	100 µg ALFQ	x	xx.x	xx.x	xx.x	xx.x, xx.x
	50 µg ALFQ	x	xx.x	xx.x	xx.x	xx.x, xx.x
[Additional visits, Fold Change from Baseline]	200 µg ALFQ	x	xx.x	xx.x	xx.x	xx.x, xx.x
	100 µg ALFQ	x	xx.x	xx.x	xx.x	xx.x, xx.x
	50 µg ALFQ	x	xx.x	xx.x	xx.x	xx.x, xx.x

Note: N = Number of participants in the Safety Population with results available

**IMMUNOGENICITY****Table 14: Durability of Immunology Response as Measured by Area Under the Response Curve, by Antigen and Vaccination Group – [Assay name]**

Antigen	200 µg ALFQ (N=X)		100 µg ALFQ (N=X)		50 µg ALFQ (N=X)		p-value a
	n	Mean (95% CI)	n	Mean (95% CI)	n	Mean (95% CI)	
gp120 A244gD-D11	xx	xx.x (xx.x, xx.x)	xx	xx.x (xx.x, xx.x)	xx	xx.x (xx.x, xx.x)	0.xx
gp120 MNgD- D11	xx	xx.x (xx.x, xx.x)	xx	xx.x (xx.x, xx.x)	xx	xx.x (xx.x, xx.x)	0.xx
[Additional antigens]							

Note: N = Number of participants in the Immunogenicity Population; n = Number of participants with available analysis values ·ANOVA used to compare mean log AUC across all vaccination groups

**Table 15: Immunology Geometric Mean Titers and Associated 95% CIs by Visit, Antigen, and Vaccination Group – [assay name]**

Visit	Antigen	200 µg ALFQ (N=X)		100 µg ALFQ (N=X)		50 µg ALFQ (N=X)		p-value
		n	GMT (95% CI)	n	GMT (95% CI)	n	GMT (95% CI)	
Baseline (Day 0)	gp120A244gD-D11	xx	xx.x (xx.x, xx.x)	xx	xx.x (xx.x, xx.x)	xx	xx.x (xx.x, xx.x)	0.xx
	[Additional antigens]	xx	xx.x (xx.x, xx.x)	xx	xx.x (xx.x, xx.x)	xx	xx.x (xx.x, xx.x)	0.xx
		xx	xx.x (xx.x, xx.x)	xx	xx.x (xx.x, xx.x)	xx	xx.x (xx.x, xx.x)	0.xx
[Additional visits or Peak]		xx	xx.x (xx.x, xx.x)	xx	xx.x (xx.x, xx.x)	Xx	xx.x (xx.x, xx.x)	0.xx

[figure not shown]
**Note:** This will be adapted for assays with continuous analysis values, as appropriate

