2.4.1. Local Reactions

Participants may exhibit post-vaccination reactions including local reactions at the injection site such as erythema, induration, pain/tenderness, swelling and limitation of arm movement. These reactions are generally of short duration and rarely require treatment. Should such reaction persist and require treatment, the participant will be referred to appropriate medical care services.

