3. OBJECTIVES AND ENDPOINTS

The objectives and associated endpoints are provided in [Table 3](#).

Table 3: Objectives and Endpoints

Objective	Endpoint
Primary:	
To evaluate the safety and tolerability (including reactogenicity) of candidate vaccine A244/B.63521 with ALFQ adjuvant at the 200 µg, 100 µg, and 50 µg doses	Evaluate the occurrence and severity of solicited local and systemic AEs following candidate vaccine administration. Evaluate the occurrence, severity, and relationship to vaccination of unsolicited AEs after candidate vaccine administration. Evaluate the occurrence of SAEs, and new-onset medical conditions. Evaluate the occurrence of AEs of special interest (AESIs) following candidate vaccine administration.
Secondary:	
To evaluate the effect of candidate vaccine A244/B.63521 with ALFQ adjuvant at the 200 µg, 100 µg, and 50 µg doses on cellular, and humoral immune responses	Compare plasma IgG binding antibodies to gp120 in terms of magnitude, durability, and area under the curve among groups with differing ALFQ doses. Characterize and assess the magnitude of cell-mediated immune responses elicited across vaccination regimens including antigen-specific CD4 and CD8 T cell responses and polyfunctionality.
Exploratory:	
To characterize B-cell functional specificities for each vaccination regimen	Characterize plasma IgG and IgA binding antibodies to HIV gp120, neutralizing antibodies,

Objective	Endpoint
Primary:	

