8.2.1.6. Unexpected Adverse Event or Unexpected Suspected Adverse Reaction

An AE or suspected adverse reaction is considered unexpected if:

- It is not listed in the IB or is not listed at the specificity or severity that has been observed
- If an IB is not required or available, is not consistent with the risk information described in the general investigational plan or elsewhere in the current application, as amended
- It is mentioned in the IB as occurring with a class of drugs or as anticipated from the pharmacological properties of the drug but is not specifically mentioned as occurring with the particular drug under investigation

For example:

- Hepatic necrosis would be unexpected (by virtue of greater severity) if the Investigator's Brochure referred only to elevated hepatic enzymes or hepatitis
- Cerebral thromboembolism and cerebral vasculitis would be unexpected (by virtue of greater specificity) if the IB listed only cerebral vascular accidents.

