9.6.2. Safety Analysis

The primary endpoints of this Phase 1 study are related to the safety, reactogenicity, and tolerability of the candidate vaccine A244/B.63521 with varying doses of ALFQ adjuvant. The occurrence and severity of SAEs, AEs, AESIs, and unsolicited AEs will be tabulated by study group and compared between and among groups.

The occurrence of local and systemic reactogenicity symptoms will be assessed as the proportions of participants experiencing such safety events along with 95% confidence intervals. Pairwise, between group comparisons will be performed. These comparisons may be performed at a two-sided $\alpha=0.05$ level, using the normal approximation to the binomial distribution or an alternate testing procedure as appropriate (e.g. Fisher's Exact test for smaller samples).

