#### **3.2. Endpoints/Outcome Measures**

##### **3.2.1. Safety Endpoints**

- Evaluate the occurrence and severity of solicited local and systemic adverse events following candidate vaccine administration.
- Evaluate the occurrence, severity, and relationship to vaccination of unsolicited adverse events after candidate vaccine administration.
- Evaluate the occurrence of serious adverse events (SAEs), and new-onset medical conditions.
- Evaluate the occurrence of adverse events of special interest (AESIs) following candidate vaccine administration.

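### SAP Table 7 compares unexpected rather than unsolicited adverse events between arms, so the promised comparison of a primary endpoint is missing if the shell is followed literally

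*SAP*

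**What the plan says.** **Endpoint.** Protocol section 3 lists among the primary endpoints "Evaluate the occurrence, severity, and relationship to vaccination of unsolicited AEs after candidate vaccine administration". SAP 3.2.1 repeats it: "Evaluate the occurrence, severity, and relationship to vaccination of unsolicited adverse events after candidate vaccine administration".

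**Promised comparison.** Protocol 9.6.2 states: "The occurrence and severity of SAEs, AEs, AESIs, and unsolicited AEs will be tabulated by study group and compared between and among groups".

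**SAP text.** Section 7.1.2 gives numbers, proportions and exact confidence intervals for unsolicited events. It names no between-arm test.

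**Table 7.** Among the safety shells (Tables 5 to 13), only this one has a p-value column. Its unsolicited block has four rows: any SAE, any AESI, "Any Related, Unexpected Adverse Event" and "Any Unexpected Adverse Event Within 28 Days of Study Vaccination".

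**Definition.** Under Protocol 8.2.1.6 an event is unexpected if, among other conditions, "It is not listed in the IB or is not listed at the specificity or severity that has been observed".

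**Solicited blocks of Table 7.** Any solicited, any systemic and any local symptom each have an overall row followed by rows for Grades 1 to 4. Every row has its own p-value. The grade rows carry the footnote "Maximum severity reported", so each participant counts in one grade only. There is no cumulative row, and SAP 7.1.1 names no ordered or trend test.

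**The concern.** Unsolicited describes how an event comes to be reported. Unexpected is a regulatory classification against the IB. The two sets overlap but are not the same, and the protocol defines the second formally, so a programmer has reason to apply that definition. The output would then lack a comparison that the protocol promises for a primary endpoint, and adding it after unblinding would be post hoc.

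The grade rows raise a smaller matter. The synopsis states the primary objective as a comparison of dose-dependent safety and reactogenicity. A participant whose worst grade rises from 1 to 2 leaves the Mild row, so a lower Mild count can mean better or worse tolerability. None of the tests uses the order of the grades or of the doses.

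**Working it through.** Table 7 is an empty shell, so there is no stated figure to reproduce. The first part is a comparison of texts; the second uses assumed counts and rates.

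**1. Which events the two rows cover.**

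| Place | Event set |
|---|---|
| Protocol section 3; SAP 3.2.1 | all unsolicited events |
| Protocol 9.6.2 | unsolicited events, compared among arms |
| Table 1 footnote 3; Protocol 8.2.2 | 28 days is the unsolicited collection window |
| SAP Table 7, last two rows | unexpected events; related and unexpected events |
| SAP Tables 5, 10 and 11 | unsolicited events by arm, no p-values |

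An example of the gap: Protocol 2.4.1 names as local reactions "erythema, induration, pain/tenderness, swelling and limitation of arm movement". Swelling and limitation of arm movement are not on the solicited list in Protocol 8.2.1.2. If the IB lists them, they are unsolicited but expected, and no Table 7 row counts them unless they are SAEs or AESIs. The IB is not among the documents, so the share of unsolicited events lost could be anything from 0 to 100%.

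For scale, Protocol 2.2.3 reports unsolicited events in 5 participants of an earlier ALFQ trial with 24 + 5 = 29 participants. That is 5/29 = 17%, or 20 × 5/29 = 3.4 participants per arm of 20.

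**2. Direction of the Mild row.** Take two opposite assumed outcomes with 20 per arm, in the order 200/100/50 µg:

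- A, 200 µg worse: none/G1/G2/G3 = 0/6/11/3, 0/10/9/1, 0/15/5/0. Grade 2 or higher is 14/10/5.
- B, 200 µg better: 14/6/0/0, 10/10/0/0, 5/15/0/0. Any symptom is 6/10/15.

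The Mild row is 6/10/15 in both, with the same three-arm exact (Fisher-Freeman-Halton) p = 0.0216. On its own the row cannot say which arm was better tolerated.

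**3. Power of the rows against an ordinal test.** The baseline is Arm 1 of that earlier trial at 200 µg (Protocol 2.2.3): 14 of 24 mild and 7 of 24 moderate, read as maximum grade, leaving 24 − 14 − 7 = 3 with none. That reading is supported because 16 participants had mild injection-site pain, more than the 14 counted as mild, so the 14 cannot mean ever mild.

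Assume cumulative odds ratios of 0.5 at 100 µg and 0.25 at 50 µg. With baseline odds o, the shifted probability is OR·o/(1 + OR·o).

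- Any symptom: o = 21/3 = 7. This gives 3.5/4.5 = 77.8% and 1.75/2.75 = 63.6%.
- Grade 2 or higher: o = 7/17 = 0.412. This gives 0.206/1.206 = 17.1% and 0.103/1.103 = 9.3%.
- Mild, by subtraction: 58.3%, then 77.8 − 17.1 = 60.7%, then 63.6 − 9.3 = 54.3%.

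Simulated power with 20 per arm at two-sided 5% (chi-square for the single rows):

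| Comparison | Power |
|---|---|
| Mild row | about 6 to 7% |
| Moderate row | about 28% |
| Any row | about 34% |
| Kruskal-Wallis on maximum grade | about 46% |
| Trend of maximum grade with dose order | about 57% |

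In about 46% of the simulated trials the 50 µg arm has at least as many Mild participants as the 200 µg arm. No one reaches Grade 3 in this illustration, so a Grade 2 or higher row equals the Moderate row and has the same 28% power. The whole gain comes from the ordinal test.

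**The case against.** **The word is a slip in a sample shell.** The block heading says unsolicited, the 28 days is the unsolicited window, and Table 5 and Listing 10 use the term unsolicited. No SAP objective, endpoint or analysis section uses expectedness to define an analysis. This stands as to the likely cause. It does not remove the need to correct a term that the protocol defines.

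**Little inferential power is at stake.** With 5/29 as the rate at 200 µg and the same assumed odds ratios, a correctly labelled unsolicited row has only about 12% power. Protocol section 9 calls the study descriptive, and unsolicited events are reported by arm in any case. This limits the consequence; Protocol 9.6.2 still promises the comparison.

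**The grade rows can be read together.** The Any row stands above them, cumulative counts can be rebuilt by addition, and Table 9 prints every grade including none. This stands: only a single-grade p-value read alone misleads, and rebuilt counts come without a p-value.

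**Stronger readings that the documents do not support.**

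- A reader might infer that Table 7 as a whole tests the wrong events. The Any solicited, systemic and local rows and the SAE and AESI rows match the endpoints.
- A reader might infer that a solicited symptom worse than the IB lists would enter the unsolicited block. The block heading excludes it.
- A reader might count a headache starting on days 15 to 28 as a lost unsolicited event. The documents do not say that a listed symptom becomes unsolicited when the diary ends.

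**Conclusion.** The labelling point holds. As written, two rows of the only safety shell with p-values compare a set defined by IB listing, and no row compares any unsolicited event or any related unsolicited event. It should be corrected, although it is probably a slip. Its numerical effect cannot be stated without the IB, and the descriptive reporting of unsolicited events is unaffected.

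The grade-row point is a secondary improvement, not an error. The ambiguity of the Mild row needs no effect-size model. The power advantage of an ordinal test (about 46 to 57%, against 34% for the Any row and 28% for the Moderate row) rests on the earlier trial's rates read as maximum grades, proportional odds, the assumed odds ratios of 0.5 and 0.25 and, for the trend test, an effect that moves in one direction with dose.

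**What to change.** **Main change.** In Table 7, replace unexpected with unsolicited in both rows, so that they read: any related unsolicited adverse event; any unsolicited adverse event within 28 days of study vaccination. Leave the Any solicited, systemic and local rows and the SAE and AESI rows as they are.

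**Secondary change.** Show the Grade 1 to 4 rows as counts without p-values. For each of the Any, Systemic and Local blocks, report one ordinal test on maximum grade across the ordered ALFQ doses, and name that test in SAP 7.1.1. A Grade 2 or higher row may be added for ease of reading.

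**Cost.** One table shell and one sentence; no new data. Single-grade p-values would no longer be reported. SAP section 11 foresees review and update before unblinding, and a change made then is still prespecified.

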**Table 16: Geometric Mean Titers and Associated 95% CIs by Visit, Antigen, and Vaccination Group – [assay name]**

Visit	Antigen	200 µg ALFQ (N=X)		100 µg ALFQ (N=X)		50 µg ALFQ (N=X)		p-value a
		n	GMT (95% CI)	n	GMT (95% CI)	n	GMT (95% CI)	
Baseline (Day 0)	CD4+ T cells all IFNy+	xx	xx.x (xx.x, xx.x)	xx	xx.x (xx.x, xx.x)	xx	xx.x (xx.x, xx.x)	0.xx
	CD4+ T cells all IL2+	xx	xx.x (xx.x, xx.x)	xx	xx.x (xx.x, xx.x)	xx	xx.x (xx.x, xx.x)	0.xx
	CD4+ T cells all IFNy and IL2	xx	xx.x (xx.x, xx.x)	xx	xx.x (xx.x, xx.x)	xx	xx.x (xx.x, xx.x)	0.xx
	CD4+ T cells all IFNy+ or IL2+	xx	xx.x (xx.x, xx.x)	xx	xx.x (xx.x, xx.x)	xx	xx.x (xx.x, xx.x)	
	CD8+ T cells all IFNy+	xx	xx.x (xx.x, xx.x)	xx	xx.x (xx.x, xx.x)	xx	xx.x (xx.x, xx.x)	
	CD8+ T cells all IL2+	xx	xx.x (xx.x, xx.x)	xx	xx.x (xx.x, xx.x)	xx	xx.x (xx.x, xx.x)	
	CD8+ T cells all IFNy and IL2	xx	xx.x (xx.x, xx.x)	xx	xx.x (xx.x, xx.x)	xx	xx.x (xx.x, xx.x)	
	CD8+ T cells all IFNy+ or IL2+	xx	xx.x (xx.x, xx.x)	xx	xx.x (xx.x, xx.x)	xx	xx.x (xx.x, xx.x)	
[Additional visits or Peak]		xx	xx.x (xx.x, xx.x)	xx	xx.x (xx.x, xx.x)	xx	xx.x (xx.x, xx.x)	0.xx

**Note:** This will be adapted for assays with continuous analysis values, as appropriate

Figure 1: CONSORT Flow Diagram

